9.10. Reporting of any deviations from the original statistical plan

In case of any deviation from the planned statistical analysis all the changes compared to the methods described in the Protocol should be identified. Similarly, if there is a need for any additional changes, upon the completion of the analysis they should be specified in the Study report.

10. ADMINISTRATIVE PROCEDURES

ک

Confidential Page 71 of 94

10.5. Ethical aspects

10.5.1. Independent Ethics Committee

Prior to the clinical study initiation, all study sites will obtain written approvals of independent Ethics committees (IECs) in accordance with International Conference on Harmonization Good Clinical Practice Guideline (ICH GCP(E6 R2)) and Eurasian Economic Union (EEU), principles provided in Helsinki Declaration, as well as in accordance with the applicable legislation and regulations of the Russian Federation. The following documents shall be submitted for IEC's review: study protocol with amendments, patient's information list and the informed consent form, written materials to be submitted to the patients, investigator's brochure, information of safety of the study drug application, information on payments and other remunerations to the patients, investigator's scientific biography and other documents at request.

The list of IEC's members and the statement of its organization and operations compliance with the standards of the Good Clinical Practice and regulatory requirements shall be submitted to the Sponsor.

10.5.2. Ethical conduct of clinical study

The procedures described in the Protocol of clinical studies related to its conduct, assessment and documentation of the findings have been designed to ensure that the Sponsor and the Investigator followed the requirements of the Good Clinical Practice guidance of International Conference on Harmonization (ICH GCP(E6 R2)) and the Eurasian Economic Union (EEU). This clinical study will also be conducted in accordance with applicable law and applicable regulatory requirements. This includes the possibility of conducting audits and inspections by representatives of the Sponsor and/or competent authorities. The Investigator should give their consent to monitoring, audits and inspections in study site and at any time on demand providing direct access to the study for the Sponsor and representatives thereof, Independent Ethics Committee and competent authorities

10.5.3. Informed Consent

Prior to the clinical study, the Investigator shall obtain IEC's written approval of the patient's information sheet and the informed consent form, as well as any other written information, which will be provided to the study subjects. IEC's written approval and approved documents shall be filed with the Study Record.

Confidential Page 72 of 94

The procedure for obtaining the informed consent shall comply with the requirements of International Conference on Harmonization Good Clinical Practice Guideline (ICH GCP(E6)) and Eurasian Economic Union (EAU), principles provided in Helsinki Declaration, as well as in accordance with the applicable legislation and regulations of the Russian Federation. The informed consent form shall be signed and dated by the patient before beginning of any study procedures. The process of obtaining the informed consent shall be described in detail in the primary documentation, including the fact of patient's consent to take part in this clinical study and the date of signing; the version of the informed consent form should be specified

		-

Confidential Page 73 of 94

1. ABBREVIATIONS

Standard Abbreviations

AE	adverse event
ANCOVA	analysis of covariance
ATC	Anatomical Therapeutic Chemical (class)
AUC	area under the curve
BDR	blind data review
BMI	body mass index
bpm	beats per minute
CRF	case report form
CRO	contract research organization
CV	coefficient of variation
DARIUS	Document And Regulatory Information Universal System
DBP	diastolic blood pressure
DDT	data definition table
DSMB	data safety monitoring board
ECG	electrocardiogram
FA	Full Analysis
FDA	food and drug administration
Geo. mean	geometric mean
GOP	global standard operating procedure
HLGT	High Level Group Term
HLT	High Level Term
IBSQOL	Irritable bowel syndrome quality of life
ICH	International Conference on Harmonization
LDA	day number of the last day of drug administration
LLOQ	lower level of quantification
LLT	Lowest Level Term
LOCF	last observation carried forward
max	maximum
MedDRA	Medical Dictionary for Regulatory Activities
min	minimum
N,n	number of observations
NA	not applicable
OC	observed cases
PD	pharmacodynamic

PK	pharmacokinetic
PP	Per Protocol
РТ	Preferred Term
QOL	quality of life
S.I.	System International
SAE	serious adverse event
SAP	statistical analysis plan
SBP	systolic blood pressure
SD	standard deviation
SOC	System Organ Class
SOP	standard operating procedure
TARC	Therapeutic Area Review Committee
TEAE	treatment-emergent adverse event
TESAE	treatment-emergent serious adverse event
TLF/T,L,F	tables, listings and figures
ULOQ	upper limit of quantification
URL	upper reference limit
WC	windowing convention
WHO-	World Health Organization – Drug Dictionary
DD(E)	(enhanced)

2. INTRODUCTION

3. SUMMARY OF THE PROTOCOL

3.1 Overall Study Plan

An open-label, randomized, comparative Phase III clinical study. The study is performed to evaluate efficacy and safety of Mebeverine+Simethicone fixed-dose combination versus Duspatalin \mathbb{R} (mebeverin) and versus Espumisan \mathbb{R} (simethicone) after 4 weeks of treatment in patients with functional bowel disorders with abdominal pain and excess gas formation.

3.2 Study Flowchart

The flowchart of the study can be found in Appendix 9.1.

3.3 Study Objectives

Primary objectives:

To assess the efficacy of Mebeverine+Simethicone fixed-dose combination versus Duspatalin® (mebeverin) and Espumisan® (simethicone) based on the change of abdominal pain and bloating/flatulence intensity, assessed with NRS-11 scales after 4 weeks of treatment in patients with functional bowel disorders with abdominal pain and bloating/flatulence.

Secondary objectives:

To evaluate the following efficacy and safety parameters of Mebeverine+Simethicone fixeddose combination versus Duspatalin® (mebeverin) and versus Espumisan® (simethicone) in patients with functional bowel disorders with abdominal pain and excess gas formation (bloating/flatulence:

- Change from baseline of NRS-11 pain intensity after 4 weeks of treatment;
- Proportion of patients with the NRS-11 pain intensity reduction of ≥30% versus baseline during at least 50% of treatment weeks over treatment period;
- Proportion of patients with the NRS-11 pain intensity reduction of ≥ 50% versus baseline during at least 50% of treatment weeks over treatment period;
- Proportion of patients with the abdominal pain assessed in the Patient Dairy completely resolved during at least 50% of treatment weeks over treatment period (NRS-11 0 assessment);
- Change from baseline of NRS-11 bloating/flatulence intensity after 4 weeks of treatment;
- Proportion of patients with the NRS-11 bloating/flatulence intensity reduction of \geq 30% versus baseline during at least 50% of treatment weeks over treatment period;
- Proportion of patients with the NRS-11 bloating/flatulence intensity reduction of \geq 50% versus baseline during at least 50% of treatment weeks over treatment period;
- Proportion of patients with the bloating/flatulence assessed in the Patient Dairy completely resolved during at least 50% of treatment weeks over treatment period (NRS-11 0 assessment);

- Change in number of days per week during study treatment period when drotaverine was taken;
- Change in quality-of-life evaluation using IBSQOL questionnaire versus baseline;
- The incidence and severity of adverse events (AE) and serious adverse events (SAE), physical examination, vital signs and lab results.

4. STATISTICAL ANALYSIS

4.1 Subject samples

There will be five subject samples.

The All Subjects Consented subject sample will consist of all subjects who:

- gave their informed consent.

The All Subjects Allocated to Treatment subject sample will consist of all subjects who:

- are in the All Subjects Consented sample;
- were allocated to treatment (randomized).

The Safety subject sample will consist of all subjects who:

- are in the All Subjects Allocated to Treatment sample;
- received at least one dose of the study product.

The Full Analysis (FA) subject sample will consist of all subjects who:

- are included in the Safety subject sample;
- have at least one post-baseline assessment of the efficacy parameters.

The Per Protocol (PP) subject sample will consist of all subjects who:

- are included in the Full Analysis sample;
- had no significant protocol violations (consideration about exclusion of patients from the PP sample will be performed at the Blind Data Review before the Data Base Lock).

4.2 Efficacy analysis

The FA subject sample will be used for the analysis of the efficacy data. Additionally, primary efficacy results analysis will be conducted on the PP sample as the sensitivity analysis. Descriptive statistics will be presented by treatment arm for all planned efficacy endpoints.

The PP subject sample analyses will be based on available data only and no missing data will be imputed.

The FA subject sample analyses will be based how on available data only so and data following the last observation carried forward (LOCF) approach will be used.All parameters will be summarized using descriptive statistics and listed.

4.2.1 Primary Efficacy Analysis

The primary efficacy endpoint is:

- Change from baseline of sum of NRS-11 abdominal pain and bloating/flatulence intensity scores after 4 weeks of treatment.

The baseline abdominal pain and bloating/flatulence intensity will be determined as the average of the NRS-11 daily assessment during 7 days before randomization (weekly average of last week of screening and run-in period, in other words, the average of - 6 to 1 days). The Week 4 assessment is the same (data from last 7 days of the corresponding week in the case duration of treatment 28 days: 23 to 29 days or data from the last 7 days before the last treatment day inclusively in the case duration of treatment did not equal 28 days.

11

For the difference of changes in sum scores of NRS-11 pain and bloating/flatulence intensities after 4 weeks of treatment versus baseline between the groups Mebeverine+Simethicone versus Duspatalin® and Mebeverine+Simethicone versus Espumisan®, a two-sided 95% confidence interval (CI) will be constructed, which is equivalent to a 97.5% one-sided CI.

The confidence interval will be constructed using ANCOVA, which will include treatment and site as fixed effect, and baseline parameter will be included in the model as covariate.

ANCOVA analysis will be performed using SAS code for the analysis:

```
ods output LSmeans=LSMeans;
ods output Diffs=CL;
proc mixed data= <dataset_name> ;
        CLASS <treatment> <site>;
        MODEL <change from bl> = <treatment> <site> <baseline>;
        lsmeans <treatment> / pdiff cl;
run;
ods output close;
```

To test the hypothesis of superiority of the FDC Mebeverine+Simethicone versus every comparator (Duspatalin® and Espumisan®), the upper confidence limit will be used.

The null hypothesis (H₀: no difference in change from baseline of sum of bloating/flatulence and pain scores between the FDC and corresponding comparator, will be rejected in favor of the alternative hypothesis (Ha: larger change from baseline of sum of bloating/flatulence and pain scores in the fixed-dose combination Mebeverine+Simethicone group) only if the upper limit of two-sided 95% CI does not contain the value 0.

In addition, the study will be considered successful in case both superiority hypothesizes are proven, i. e. upper limit of two-sided 95% CI does not contain the value 0 for both constructed confidence intervals. In this case, a conclusion will be drawn on the fixed-dose combination of Mebeverine+Simethicone is superior versus Duspatalin® (mebeverin) and Espumisan® (simethicone) for the pooled decrease of pain and bloating/flatulence intensity.

As a Sensitivity analysis # 1, PP subject sample will be used for analysis of the primary endpoint.

Sensitivity analysis # 2, LOCF method - one the FA subject sample will be used for analysis of the primary endpoint.

ANCOVA analysis will be performed using SAS code for the sensitivity analyses # 1 and # 2:

ods output LSmeans=LSMeans;

Missing values will be imputed using: the nearest previous post-baseline non-missing value for treatment period, the EoT or the nearest previous follow-up non-missing value for follow-up period. If patient has a missing value after such an imputation applying, his/her ALT response will be considered as failure.

Source: NST001, NSL010, NSL017.

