3.3. Study treatment period

3.3.1. Visit 2, Randomization (Week 0, Day 1)

On Visit 2 (Week 0, Day 1) patients who meets all inclusion/exclusion criteria, will be randomized into one of the three groups at a 1:1:1 ratio. Vital signs, body weight, AEs and concomitant medication will be evaluated. Patients will assess their quality of life by completing IBSQOL.

Group	Study product	Number of patients	
1	Mebeverine+Simethicone, 135 mg+80 mg, three times a day	155	
2	Duspatalin® 135 mg three times a day	155	
3	Espumisan®, 80 mg (2 capsules 40 mg) three times a day	155	

Confidential Page 28 of 94

The study will be open, with no treatment blinding.

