3.5.2. Study treatment duration and dosage regimen

To develop a fixed-dose combination, standard doses of Mebeverine and Simethicone studied in clinical trials and long used in clinical practice as per the Duspatalin® and Espumisan® prescribing information were used.

FDC Mebeverin+Simethicone is designed for symptomatic treatment of abdominal pain and bloating in patients with FBD. The FDC is used in this patient population for the purpose of symptoms relief, but not for the resolution of the main cause of the disease.

To improve the quality of life in patients with FBD it is necessary to decrease rapidly the main symptoms: abdominal pain and bloating. FDC Mebeverin+Simethicone is designed for relief of such symptoms as abdominal pain and bloating, and the quick therapeutic response is expected. The expectation of quick therapeutic response is based on the published data from clinical studies, which demonstrated that treatment with antispasmodic and simethicone in patients with IBS (in line with diagnostic criteria established before Rome IV classification, that is why this population includes not only patients with IBS but also patients with other functional bowel disorders as per Rome IV criteria) leads to the pain and bloating decrease as early as after 4 weeks of therapy. 50,51,52,53,54,55,56,57,58,59,60,61 These data are in consistence with published recommendations on clinical studies design in patients with functional GIT disorders, in which the minimal duration of study treatment for symptomatic drugs was defined as 4 weeks (but not for the drugs developed for the chronic long-term basic therapy. ⁶² As the FDC Mebeverin+Simethicone was developed as symptomatic drug for patients with functional GIT disorders, the 4 weeks duration therapy was chosen for the planned study. Abdominal pain and bloating relief with the FDC Mebeverin+Simethicone treatment are expected at the end of 4 weeks period. The long-term study treatment with the FDC in comparison with mebeverin monotherapy and simethicone monotherapy seems to be not rational as the therapeutic effect of each mono-component occurs after first dose already, and treatment with simethicone and mebeverin as mono-components does not allow to control symptoms of the disease sufficiently and increases the risk for postponed abdominal pain and bloating relief.

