5.3. Compliance of the therapy conduction

The patient should take the first study drug dose at the Visit 2 day (Week 0). During telephone contact (TC 1, Week 2, Day 0), the Investigator checks the patient's treatment compliance and whether he/she follows the recommendations on the Patient's Diary filling, and, if necessary, conducts an additional conversation with the patient about the proper drug administration and filling out the Patient's Diary. At Visit 3 (Week 4, Day 29), the patient should return all used and unused study drug packagings. The Investigator will check compliance with the recommendations for study drug self-administration at Visit 3 (Week 4, Day 29) based on the results of accounting for the returned study drug and the patient's diary.

The study drug compliance will be calculated at Visit 3 using the formula:

Compliance = (N dispensed. - N returned.) / N calc. x 100%

where N dispensed. = number of tablets/capsules dispensed, N returned. = number of tablets/capsules returned, N calc. = estimated number of tablets/capsules the volunteer was to receive since the previous visit.

The compliance should be within the interval from 80% to 120%.

Confidential Page 51 of 94

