9.7. Efficacy analysis

9.7.1. Primary efficacy end point

• Change from baseline of sum of NRS-11 abdominal pain and bloating/flatulence intensity scores after 4 weeks of treatment.

The baseline abdominal pain and bloating/flatulence intensity will be determined as the average of the NRS-11 daily assessment during 7 days before randomization (weekly average of last week of screening and run-in period). The Week 4 assessment is the same (data from last 7 days of the corresponding week)..

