The baseline abdominal pain and bloating/flatulence intensity will be determined as the average of daily episodes NRS-11 assessment during 7 days before randomization (last week of screening and run-in period, in other words, the average of daily episodes from - 6 to 1 days). The data from the last week of screening and run-in period will be also used for baseline assessment of stool frequency and consistency and number of days of drotaverine intake. Week 1 (average of data 2 - 8 days), Week 2 (average of data 9 - 15 days), Week 3 (average of data 16 - 22 days) and Week 4 (average of data from the last 7 days of the corresponding week in the case duration of treatment 28 days: 23 to 29 days or data from the last 7 days before the last treatment day inclusively in the case duration of treatment did not equal 28 days).

The proportion of patients with the *Scale* reduction of $\geq A\%$ versus baseline during at least 50% of treatment weeks over treatment period must be calculated as:

$$\frac{n_T}{N_T}$$

where N_T is total number of patients in the treatment arm T, n_T is number of patients in the treatment arm T who had reduction of $\ge A\%$ versus baseline (week 0) during at least 2 of treatment weeks over treatment period: week 1, week 2, week 3, week 4). Reduction of $\ge A\%$ must calculate as:

$$Reduction_{i} = \frac{\overline{Scale_{Week_{i}}} - \overline{Scale_{Week_{0}}}}{\overline{Scale_{Week_{0}}}} \times 100 \ge A\%$$

The transformation formula used for the IBS-QOL total and scale scores is:

 $Score = \frac{The sum of the items - lowest possible score}{Possible raw score range} \times 100$

Where

lowest possible score = number of questions \times lowest possible score of the items

possible raw score range

= number of questions

 \times (upper possible score of the items - lowest possible score of the items)

The comparisons of treatment arms for secondary endpoints with "Proportion of patients with the..." type will be analyzed using Fisher exact test. The test will be performed by separately for for Mebeverine + Simethicone combination VS Duspatalin (mebeverin) and Mebeverine + Simethicone combination VS Espumisan (simethicone) comparisons.

Fisher exact test will be performed using following SAS code for the analysis:

```
PROC FREQ DATA = [dataset name];
  weight [frequency var] / ZEROS;
  tables [frequency var lvl 1/ frequency var lvl 2] * [Arm] / exact Fisher;
RUN;
```

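### The SAP's baseline window (Days -6 to 1) includes the day of randomization and first dose, and neither document clearly requires the Day 1 diary rating to be made before dosing

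*SAP*

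**What the plan says.** Protocol 9.7.1 defines baseline as "the average of the NRS-11 daily assessment during 7 days before randomization". Protocol 3.2.1 and 6.8 use the same seven days for the 4-to-9 entry criteria on pain and bloating.

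SAP 4.2.1 repeats the protocol's definition and then translates it into study days: "in other words, the average of - 6 to 1 days". SAP 4.2.2 does the same for the secondary endpoints: "the average of daily episodes from - 6 to 1 days".

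Day 1 is the randomization visit. Protocol 3.3.1 states: "On Visit 2 (Week 0, Day 1) patients who meets all inclusion/exclusion criteria, will be randomized into one of the three groups". Protocol 5.3 puts the first dose on that same day, and SAP 6.1.5 ties relative Day 1 to the first drug administration. SAP 6.1.1 lists Day 1 in both the screening period and the treatment period. The study is open-label, so the patient knows the arm from Visit 2 on.

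Each daily rating covers the worst episode of the preceding 24 hours (Protocol Table 1, footnotes 4 and 5). No clock time is set for the diary entry. The SAP's later windows are Days 2–8 for Week 1 and Days 23–29 for Week 4.

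**The concern.** The SAP sentence gives two definitions that agree only if the Day 1 rating is made before treatment starts. If a patient fills in the Day 1 entry at home that evening, it is made with the arm known and probably after one or more doses. The protocol itself expects a fast response, stating that "the therapeutic effect of each mono-component occurs after first dose already".

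Baseline has three uses in the efficacy analysis. It is subtracted in the primary change score, it is the ANCOVA covariate, and it is the denominator of the 30% and 50% responder percentages. If part of it is measured after randomization, treatment or expectation can move it differently by arm, and randomization no longer protects the adjusted comparison. The analysed baseline could also differ from the value on which the patient was admitted to the trial.

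**Working it through.** **Which days the window covers.** With no Day 0, Days -6 to 1 are -6, -5, -4, -3, -2, -1 and 1. That is seven days, one of them Day 1. Reading the window as -6 to -1 gives only six days, so a lost minus sign does not explain it. Week 1 starts on Day 2, which confirms that Day 1 is assigned to baseline. Its weight is 1/7, about 14%.

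**What the ratings describe.** If each rating is made before that day's dosing and looks back 24 hours, ratings on Days -6 to 1 describe Days -7 to -1. Ratings on Days 2–8 describe Days 1–7, and ratings on Days 23–29 describe Days 22–28. On that reading all windows share a one-day lag and the baseline is the protocol's. The reading fails for any patient whose Day 1 entry follows the dose.

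**The plan's own figures (Protocol 9.2).** Inputs are a difference of 1.0, SD 2.5, two-sided alpha 0.05 and 132 per group.

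- Standard error = 2.5 × √(2/132) = 0.308.
- Power = Φ(1.0/0.308 − 1.96) = 90.1%, against 90% stated.
- Power for both comparisons = 0.901² = 81.3% if they were independent, or 83.5% with correlation 0.5 for the shared combination arm, against about 80% stated.

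**Effect of a post-dose Day 1 rating.** Let d be the between-arm difference in the Day 1 sum score, and let the slope be that of the Week 4 score on baseline. A slope of 1.0 is the unadjusted change score. The baseline difference is d/7, so

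estimate = Week 4 difference − slope × d/7.

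The documents give neither d nor the slope. I assume d of 0.5 to 1.0, a slope of 0.3 to 1.0, every Day 1 entry post-dose and a true Week 4 difference of 1.0. Power for both comparisons uses correlation 0.5 and the same d against each comparator.

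| Day 1 difference | Slope | Shift | Estimate | Power, one comparison | Power, both |
|---|---|---|---|---|---|
| 0.5, favours combination | 0.3 | 0.021 | 0.979 | 88.9% | 81.5% |
| 0.5, favours combination | 1.0 | 0.071 | 0.929 | 85.5% | 76.5% |
| 1.0, favours combination | 0.3 | 0.043 | 0.957 | 87.5% | 79.4% |
| 1.0, favours combination | 1.0 | 0.143 | 0.857 | 79.5% | 68.1% |
| 0.5, favours comparator | 0.3 | 0.021 | 1.021 | 91.3% | 85.3% |
| 1.0, favours comparator | 1.0 | 0.143 | 1.143 | 96.0% | 92.9% |

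With d = 0 the shift is zero, whatever the slope.

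**The case against.** The benign reading is strong. Protocol 7.2.1 lists the NRS-11 evaluation, diary review and eligibility check ahead of randomization and drug dispensing, so a Visit 2 rating is naturally pre-dose. With 24-hour recall it describes the day before randomization. The last dose is due the evening before Day 29 (Protocol 5.2), so Days 23–29 follow the same lag at the end of treatment. Protocol 7.1 also asks for scales to be completed before dosing. All this stands as evidence of intent. It does not settle the timing: the 7.1 sentence is in the screening section and concerns scales completed with site staff, and nothing clearly extends it to the home diary entry on Day 1.

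Three stronger readings are tempting but not supported.

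- A reader might infer that the baseline does contain post-dose ratings. The documents show only that it can.
- A reader might infer a serious loss of power. Getting from 90% to 64% takes a 2-point Day 1 gap, twice the planned Week 4 effect, with a slope of 1 (estimate 1 − 2/7 = 0.714). The protocol's remark about an effect from the first dose concerns each mono-component and does not imply an early gap between arms. A gap favouring the combination would in any case dilute its effect, which is conservative for superiority.
- A reader might infer that the window should simply become Days -7 to -1, or that it has eight days because of a Day 0. Day -7 is the nominal Visit 1, when the diary is handed out and the NRS-11 rating listed in Protocol 7.1 covers three months. Patients on the standard schedule may therefore have no 24-hour rating for that day. Neither document uses a Day 0 on this scale.

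**Conclusion.** The point holds as a gap in the definition of the primary baseline. The SAP's study-day window includes the day of randomization and first dose, and no clear rule keeps a post-dose rating made with the arm known out of the baseline.

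The likely size is small. Under the stated assumptions the estimate moves by about 0.02 to 0.14 of the planned 1.0 point, in either direction. If the Day 1 difference favours the combination, power per comparison falls from 90% to about 89%–80%. If it favours the comparator, the estimated benefit is inflated by the same amounts. These figures treat every Day 1 entry as post-dose, so a mixture of timings gives less. There is no bias if all Day 1 entries were made before dosing. Because the direction is unknown, the rule should be settled before database lock.

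**What to change.** In SAP 4.2.1 and 4.2.2, define baseline as the mean of the last 7 daily diary ratings completed before randomization and first dose. Keep the Day 1 entry only if its recorded time precedes the first dose. Otherwise replace it with the Day -7 rating, if a 24-hour rating exists for that day, or average the remaining 6. Use this one value for eligibility checks, change scores, responder percentages and the covariate. Protocol 9.2 says recruitment was complete at Amendment 1, so the eligibility check is now a retrospective one.

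The cost is a few lines of SAP text, with no new data and no change to the 132 or 155 per group. SAP 4.3.5 lists a time of assessment for the NRS-11 and SAP 4.3.8 lists the time of each administration, so the check looks feasible. The sponsor should confirm that the NRS-11 time is a clock time. If it is not, Day 1 entries cannot be shown to be pre-dose and fall under the replacement rule. The downside is that some patients will have 6 baseline ratings instead of 7.
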